10.3.3. Adverse Events of Interest

Liver disorder is considered a potential risk and will be closely monitored. As such, liver events have been deemed of interest in the GB001 program.

Adverse events of interest will include alanine aminotransferase increased, aspartate aminotransferase increased, blood bilirubin increased and/or associated preferred terms alone or associated with other conditions of concern, that result in temporary or permanent

discontinuation of IP as defined in Appendix 6 ([Section 10.6, Table 6](#)) with the exception of events for which subjects cannot be monitored. Follow-up liver laboratory values ([Table 4](#)), Appendix 2 [[Section 10.2](#)]) and additional information to characterize the etiology of the event are mandatory and specified in Appendix 6 ([Section 10.6, Table 6](#)).

10.3.4. Recording and Follow Up of Adverse Events and Serious Adverse Events

AE and SAE Recording

- When an AE/SAE occurs, it is the responsibility of the investigator to review all documentation (eg, hospital progress notes, laboratory reports, and diagnostics reports) related to the event.
- The investigator will then record all relevant AE/SAE/AE of Interest information in the eCRF.
- It is **not** acceptable for the investigator to send photocopies of the subject's medical records to the Sponsor in lieu of completion of the AE/SAE eCRF page.
- There may be instances when copies of medical records for certain cases are requested by the Sponsor. In this case, all subject identifiers, with the exception of the subject number, will be redacted on the copies of the medical records before submission to the Sponsor.
- The investigator will attempt to establish a diagnosis of the event based on signs, symptoms, and/or other clinical information. Whenever possible, the diagnosis (not the individual signs/symptoms) will be documented as the AE/SAE.

Assessment of Intensity

The investigator will assess intensity for each AE and SAE reported during the study and assign it to 1 of the following categories:

- Mild: An event that is easily tolerated by the subject, causing minimal discomfort and not interfering with everyday activities.
- Moderate: An event that causes sufficient discomfort and interferes with normal everyday activities.
- Severe: An event that prevents normal everyday activities. An AE that is assessed as severe should not be confused with a SAE. Severe is a category utilized for rating the intensity of an event; and both AEs and SAEs can be assessed as severe.

An event is defined as 'serious' when it meets at least 1 of the predefined outcomes as described in the definition of an SAE, NOT when it is rated as severe.

Assessment of Causality

- The investigator is obligated to assess the relationship between IP and each occurrence of each AE/SAE.
 - **Related** – The AE is known to occur with the IP, there is a reasonable possibility that the IP caused the AE, or there is a temporal relationship between the IP and event. Reasonable possibility means that there is evidence to suggest a causal relationship between the IP and the AE.
 - **Not Related** – There is not a reasonable possibility that the administration of the IP caused the event, there is no temporal relationship between the IP and event onset, or an alternate etiology has been established.
- The investigator will use clinical judgment to determine the relationship.
- Alternative causes, such as underlying disease(s), concomitant therapy, and other risk factors, as well as the temporal relationship of the event to IP administration will be considered and investigated.
- The investigator will also consult the Investigator's Brochure (IB) and/or Product Information, for marketed products, in his/her assessment.
- For each AE/SAE, the investigator **must** document in the medical notes that he/she has reviewed the AE/SAE and has provided an assessment of causality.
- There may be situations in which an SAE has occurred, and the investigator has minimal information to include in the initial report to the Sponsor. However, **it is very important that the investigator always assess causality for every event before the initial transmission of the SAE data to the Sponsor.**
- The investigator may change his/her opinion of causality in light of follow-up information and send a SAE follow-up report with the updated causality assessment.
- The causality assessment is one of the criteria used when determining regulatory reporting requirements.

[figure not shown]
Follow-up of AEs and SAEs

- The investigator is obligated to perform or arrange for the conduct of supplemental measurements and/or evaluations as medically indicated or as requested by the Sponsor to elucidate the nature and/or causality of the AE or SAE as fully as possible. This may include additional laboratory tests or investigations, histopathological examinations, or consultation with other health care professionals.
- If a subject dies during participation in the study or during a recognized follow-up period, the investigator will provide the Sponsor with a copy of any post-mortem findings including histopathology if available.
- New or updated information will be recorded in the originally completed eCRF.
- The investigator will submit any updated SAE data to the Sponsor within 24 hours of receipt of the information.

10.3.5. Reporting of SAEs

SAE Reporting to the Sponsor via an Electronic Data Collection Tool

- The mechanism for reporting an SAE to the Sponsor will be the electronic data capture system.
- If the electronic system is unavailable, then the site will contact the Medical Monitor in order to report the event and submit the paper SAE report form via the contacts below within 24 hours.
- The site will enter the SAE data into the electronic system as soon as it becomes available.
- After the study is completed at a given site, the electronic data collection tool will be taken off-line to prevent the entry of new data or changes to existing data.
- If a site receives a report of a new SAE from a study subject or receives updated data on a previously reported SAE after the electronic data collection tool has been taken off-line, then the site can report this information via contact to the Medical Monitor and submitting the paper SAE report form via the contacts below.
- Contacts for SAE reporting can be found below.

10.4. Appendix 4: Contraceptive Guidance and Collection of Pregnancy Information

Definitions:

Woman of Childbearing Potential (WOCBP)

A woman is considered fertile following menarche and until becoming post-menopausal unless permanently sterile (see below).

If fertility is unclear (eg, amenorrhea in adolescents or athletes) and a menstrual cycle cannot be confirmed before first dose of IP, additional evaluation should be considered.

Women in the following categories are not considered WOCBP

1. Premenarchal
2. Premenopausal female with 1 of the following:
 - Documented hysterectomy
 - Documented bilateral salpingectomy
 - Documented bilateral oophorectomy

For individuals with permanent infertility due to an alternate medical cause other than the above, (eg, mullerian agenesis, androgen insensitivity), investigator discretion should be applied to determining study entry.

Note: Documentation can come from the site personnel's: review of the subject's medical records, medical examination, or medical history interview.

3. Postmenopausal female
 - A postmenopausal state is defined as no menses for 12 months without an alternative medical cause.
 - A high follicle stimulating hormone (FSH) level (eg, > 40 IU/L) in the postmenopausal range may be used to confirm a postmenopausal state in women not using hormonal contraception or hormonal replacement therapy (HRT). However, in the absence of 12 months of amenorrhea, confirmation with more than one FSH measurement is required.
 - Females on HRT and whose menopausal status is in doubt will be required to use one of the non-estrogen hormonal highly effective contraception methods if they wish to continue their HRT during the study. Otherwise, they must discontinue HRT to allow confirmation of postmenopausal status before study enrollment.

Contraception Guidance:

- A female subject is eligible to participate if she is not pregnant or breastfeeding, and at least one of the following conditions applies:
 - Is not a woman of childbearing potential (WOCBP)

OR

 - Is a WOCBP and using a contraceptive method that is highly effective (with a failure rate of < 1% per year), preferably with low user dependency (see table below), at least 1 month prior to Screening, during the intervention period, and for 28 days after the last dose of IP, and agrees not to donate eggs (ova, oocytes) for the purpose of reproduction during this period. The investigator should evaluate the effectiveness of the contraceptive method in relationship to the first dose of IP.
 - A WOCBP must have a negative highly sensitive pregnancy test (urine or serum as required by local regulations) within 24 hours before the first dose of IP.
 - If a urine test cannot be confirmed as negative (eg, an ambiguous result), a serum pregnancy test is required. In such cases, the subject must be excluded from participation if the serum pregnancy result is positive.

Contraceptive use should be consistent with local regulations regarding the use of contraceptive methods for those participating in clinical studies.

Highly Effective Methods^a That Have Low User Dependency

• Implantable progestogen-only hormone contraception associated with inhibition of ovulation^b

• Intrauterine device (IUD)

• Intrauterine hormone-releasing system (IUS)^b

• Bilateral tubal occlusion

• Vasectomized partner

• (Vasectomized partner is a highly effective contraceptive method provided that the partner is the sole sexual partner of the woman of childbearing potential and the absence of sperm has been confirmed. If not, an additional highly effective method of contraception should be used. Spermatogenesis cycle is approximately 90 days.)
Highly Effective Methods^a That Are User Dependent

• Combined (estrogen- and progestogen-containing) hormonal contraception associated with inhibition of ovulation
– oral– intravaginal– transdermal– injectable

• Progestogen-only hormone contraception associated with inhibition of ovulation^b
– oral– injectable

• Sexual abstinence

(Sexual abstinence is considered a highly effective method only if defined as refraining from heterosexual intercourse during the entire period of risk associated with the IP. The reliability of sexual abstinence needs to be evaluated in relation to the duration of the study and the preferred and usual lifestyle of the subject.)

^a Failure rate of < 1% per year when used consistently and correctly. Typical use failure rates differ from those when used consistently and correctly

^b If locally required, in accordance with Clinical Trial Facilitation Group (CTFG) guidelines, acceptable contraceptive methods are limited to those which inhibit ovulation as the primary mode of action

Note: Periodic abstinence (calendar, symptothermal, post-ovulation methods), withdrawal (coitus interruptus), spermicides only, and lactational amenorrhoea method (LAM) are not acceptable methods of contraception for this study. Male condom and female condom should not be used together (due to risk of failure with friction).

Collection of Pregnancy Information

Female Subjects who become pregnant

- The investigator will collect pregnancy information on any female subject who becomes pregnant while participating in this study. Information will be recorded on the appropriate form and submitted to the sponsor within 24 hours of learning of a subject's pregnancy.
- The subject will be followed to determine the outcome of the pregnancy. The investigator will collect follow-up information on the subject and the neonate and the information will be forwarded to the sponsor. Generally, follow-up will not be required for longer than 6 to 8 weeks beyond the estimated delivery date. Any termination of pregnancy will be reported, regardless of fetal status (presence or absence of anomalies) or indication for the procedure.
- While pregnancy itself is not considered to be an AE or SAE, any pregnancy complication or elective termination of a pregnancy will be reported as an AE or SAE. A spontaneous abortion is always considered to be an SAE and will be reported as such. Any post-study pregnancy related SAE considered reasonably related to the study intervention by the investigator will be reported to the sponsor as described in [Section 10.3.5](#). While the investigator is not obligated to actively seek this information in former study subjects, he or she may learn of an SAE through spontaneous reporting.
- Any female subject who becomes pregnant while participating in the study will discontinue IP or be withdrawn from the study.

10.5. Appendix 5: Genetics

Use and Analysis of DNA

- Genetic variation may impact a subject's response to IP, susceptibility to, and severity and progression of disease. Variable response to IP may be due to genetic determinants that impact drug absorption, distribution, metabolism, and excretion; mechanism of action of the drug; disease etiology; and/or molecular subtype of the disease being treated. Therefore, where local regulations and IRB/IEC allow, a biosample may be collected for DNA analysis from consenting subjects.
- DNA samples may be used for research related to the relationship between safety, efficacy, and exposure parameters collected in this study, as they related to placebo, GB001, CRS, and related diseases. They may also be used to develop tests/assays including diagnostic tests related to GB001 and DP₂ inhibitors and/or atopic disease.
- Genetic research may consist of the analysis of candidate polymorphisms, prespecified in the statistical analysis plan.
- The samples may be analyzed as part of a multi-study assessment of genetic factors involved in the response to GB001 of this class to understand study disease or related atopic conditions.
- The results of genetic analyses may be reported in a separate study summary.
- The Sponsor will store the samples in a secure storage space with adequate measures to protect confidentiality.
- The samples will be retained while research on GB001 continues but no longer than 8 years or other period as per local requirements.

10.6. Appendix 6: Liver Safety - Actions and Follow-up Assessments

Liver chemistry will be evaluated as specified in the SoA ([Section 1.3](#)) and Appendix 2 ([Section 10.2](#)). Parameters will include ALT, AST, GGT, bilirubin, total bile acids, and ALP.

For subjects with ALT or AST $> 1 \times \text{ULN}$ and $< 3 \times \text{ULN}$ or total bilirubin or direct bilirubin $> 1 \times \text{ULN}$ and $\leq 1.5 \times \text{ULN}$, confirm the value within 24 to 48 hours. Contact the Medical Monitor to determine the appropriate liver monitoring schedule (eg, weekly or twice a week).

The criteria requiring additional liver monitoring with possible interruption of study intervention are detailed in [Table 5](#).

Table 5: Liver Chemistry Criteria Requiring Additional Monitoring with Possible Interruption of Investigational Product

Criterion	Actions
ALT or AST $\geq 3 \times \text{ULN}$ and $< 5 \times \text{ULN}$ or total bilirubin or direct bilirubin $> 1.5 \times \text{ULN}$ without symptoms believed to be related to liver injury or hypersensitivity, and who can be monitored weekly for 4 weeks	
Notify the Medical Monitor within 24 hours of learning of the abnormality to discuss subject safety. “Additional Liver Panel” in Table 6 may be requested by the Medical MonitorConfirm values within 24 to 48 hours via repeat labs. If unable to obtain repeat labs within 48 hours, discontinue IP.Decision to continue or interrupt study intervention will be determined by the Investigator and the Medical MonitorSubject must return weekly or more frequently for repeat liver chemistry tests (ALT, AST, GGT, ALP, total bile acids, and bilirubin) until the abnormalities resolve, stabilize, or return to baseline.If at any time the subject meets liver chemistry interruption criteria (as specified in Table 6), then follow the instructions in “Actions and Follow-up Assessments” in Table 6 and in consultation with the Medical Monitor initiate relevant assessment procedures.

In the case of AEs of interest ([Section 10.3.3](#)), potential re-challenge will be restricted to potential DILI cases that have been assessed as unlikely or not related to IP by the HAC and after liver enzymes have returned to baseline levels. When re-challenging with IP, obtain repeat liver chemistries twice weekly in the first 2 weeks and then weekly for 6 weeks after the re-challenge. If there is a rise in liver enzymes $> 2 \times \text{ULN}$, the IP should be discontinued permanently.

The criteria requiring interruption of IP with additional liver monitoring is detailed in [Table 6](#).

Table 6: Liver Chemistry Criteria Requiring Investigational Product Interruption and Additional Monitoring

Liver Chemistry – IP Interruption Criteria	
ALT/AST (single occurrence)	ALT or AST $\geq 5 \times$ ULN
ALT/AST	ALT or AST $\geq 3 \times$ ULN persists for ≥ 4 weeks
+ Bilirubin ^{a,b}	ALT or AST $\geq 3 \times$ ULN and bilirubin $> 2 \times$ ULN ($> 35\%$ direct bilirubin)
+ INR ^b	ALT or AST $\geq 3 \times$ ULN and international normalized ratio (INR) > 1.5 , if INR measured
+ Cannot Monitor	ALT or AST $\geq 3 \times$ ULN and cannot be monitored weekly for 4 weeks
+ Symptomatic ^c	ALT or AST $\geq 3 \times$ ULN associated with symptoms (new or worsening) believed to be related to liver injury or hypersensitivity
Actions and Follow-up Assessments	
Actions	Follow-Up Assessments

 Immediately discontinue IP Report the event to the Medical Monitor within 24 hours Complete the liver event eCRF and complete an SAE data collection tool if the event also met the criteria for an SAE^b Perform liver chemistry follow-up assessments. Monitor the subject until liver chemistry test abnormalities resolve, stabilize, or return to baseline (see MONITORING) Do not restart/rechallenge subject with IP unless Medical Monitor approval is granted If restart/rechallenge not granted, permanently discontinue IP and continue subject in the study for any protocol specified follow up assessments 
MONITORING:
 
 Repeat liver chemistry tests (include ALT, AST, GGT, alkaline phosphatase, total bile acids, bilirubin, and INR) and perform liver event follow-up assessments within 24 hours Monitor subject twice weekly until liver chemistry test abnormalities resolve, stabilize, or return to baseline A specialist or hepatology consultation is recommended 	
Additional Liver Panel
 
 Viral hepatitis serology ^d Obtain INR and recheck with each liver chemistry assessment until the ALT and/or AST values show downward trend Obtain blood sample for pharmacokinetic (PK) analysis Serum creatine phosphokinase (CPK) and lactate dehydrogenase (LDH) Fractionate bilirubin, if total bilirubin $> 2 \times$ ULN Obtain complete blood count with differential to assess eosinophilia Record the appearance or worsening of clinical symptoms of liver injury, or hypersensitivity, on the adverse event (AE) report form Record use of concomitant medications (including acetaminophen, herbal remedies, and other over-the-counter medications) on the concomitant medications eCRF Record alcohol use on the liver event alcohol intake eCRF Anti-nuclear antibody, anti-smooth muscle antibody, Type 1 anti-liver kidney microsomal antibodies, and quantitative total immunoglobulin G (IgG) or gamma globulins Serum acetaminophen assay Liver imaging (ultrasound, magnetic resonance, or computerized tomography) and/or liver biopsy to evaluate liver disease

[figure not shown]
a. Serum bilirubin fractionation should be performed if testing is available. If serum bilirubin fractionation is not immediately available, discontinue IP if ALT or AST $\geq 3 \times$ ULN **and** bilirubin $> 2 \times$ ULN. Additionally, if serum bilirubin fractionation testing is unavailable, **record the absence/presence of detectable urinary bilirubin on dipstick** which is indicative of direct bilirubin elevations suggesting liver injury.

- b. All events of ALT or AST $\geq 3 \times$ ULN **and** bilirubin $> 2 \times$ ULN ($> 35\%$ direct bilirubin) or ALT or AST $\geq 3 \times$ ULN **and** INR > 1.5 may indicate severe liver injury (**possible 'Hy's Law'**) **and must be reported as an SAE (excluding studies of hepatic impairment or cirrhosis)**. The INR stated threshold value will not apply to subjects receiving anticoagulants. INR is not part of routine laboratory assessments in this study.
- c. New or worsening symptoms believed to be related to liver injury (such as fatigue, nausea, vomiting, right upper quadrant pain or tenderness, or jaundice) or hypersensitivity (such as fever, rash, or eosinophilia).
- d. Includes: expanded viral hepatitis serology (Section 10.2 [Table 4](#))

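### Low-cost improvement: Table 5 does not require INR at ALT/AST 3 to < 5 x ULN, so Table 6's INR stop criterion may go unassessed while dosing continues

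*Protocol*

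**What the plan says.** Protocol Appendix 6 (Section 10.6) handles raised liver chemistry in two tiers.

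**Table 5** allows IP to continue. For ALT or AST of at least 3 and below 5 x ULN it covers subjects "without symptoms believed to be related to liver injury or hypersensitivity, and who can be monitored weekly for 4 weeks". The site must notify "the Medical Monitor within 24 hours of learning of the abnormality to discuss subject safety" and must confirm "values within 24 to 48 hours via repeat labs". "If unable to obtain repeat labs within 48 hours, discontinue" IP. The Investigator and the Medical Monitor decide together whether dosing goes on. Follow-up is at least weekly, with "repeat liver chemistry tests (ALT, AST, GGT, ALP, total bile acids, and bilirubin"; INR is not on the list. The Additional Liver Panel, which does contain INR, "in Table 6 may be requested by the Medical" Monitor.

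**Table 6** requires IP interruption. One row is ALT or AST of at least 3 x ULN with "international normalized ratio (INR) > 1.5 , if INR measured". Footnote b classes that combination as possible Hy's Law and requires an SAE report, exempts subjects on anticoagulants from the INR threshold, and states that INR is not a routine test in this study. Once any Table 6 row is met, INR joins the required monitoring tests.

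The Schedule of Activities (Section 1.3) has INR at Visit 2 only. Section 2.3.1 names drug-induced liver injury as a potential risk of GB001 because of two Hy's Law cases, one of them still blinded.

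**The concern.** The sponsor chose INR above 1.5, with raised transaminases, as a stop signal that does not depend on bilirubin. In the group where that signal could change what happens, the plan does not require the measurement.

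In a Table 5 subject, an INR above 1.5 would bring immediate IP interruption, an SAE report under footnote b, adverse-event-of-interest status (Section 10.3.3 ties this to discontinuation under Table 6) and the compulsory etiology work-up. If no INR is drawn and no other row is met, this route to those four consequences stays closed. The Investigator and Medical Monitor would then be deciding on continued dosing without a result that the protocol itself treats as decisive.

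**Working it through.** The plan gives no figure to reproduce on this point. The check traces each place where INR appears and asks whether any rule requires it for a Table 5 subject still on IP.

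1. **Scheduled tests.** After the first dose and through Week 16, clinical chemistry is scheduled at Weeks 1, 2, 3, 4, 5, 6, 8, 12 and 16, which is 9 visits. INR is scheduled at 0 of the 9.

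2. **What the INR row adds to Table 6.** These rows interrupt IP without an INR:
   - ALT or AST at least 5 x ULN;
   - at least 3 x ULN persisting for 4 weeks or more;
   - at least 3 x ULN with bilirubin above 2 x ULN (more than 35% direct);
   - at least 3 x ULN in a subject who cannot be monitored weekly;
   - at least 3 x ULN "associated with symptoms (new or worsening) believed to be related to liver injury or hypersensitivity".

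   What remains for the INR row is the Table 5 group: 3 to < 5 x ULN, for under 4 weeks, without symptoms, able to attend weekly, and with no qualifying bilirubin rise. There are two narrow exceptions. Stable pre-existing liver symptoms fall outside Table 5 and also outside the new-or-worsening row. The pre-dose Visit 2 sample already includes INR. Both are limited by exclusion criterion 5 (known liver disorders) and by randomization criterion 6 (screening ALT and AST no higher than 1 x ULN).

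3. **Test lists side by side.** Table 5 weekly: ALT, AST, GGT, ALP, total bile acids, bilirubin. Table 6 monitoring: the same six plus INR.

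4. **Other routes to an INR.** The Medical Monitor may request the panel (Table 5). The investigator may add tests at any time (Appendix 2). Appendix 2, Table 4, includes INR but is collected only when liver safety actions call for it. Section 10.3.3 makes follow-up liver tests mandatory, but for events that led to discontinuation under Table 6. None of these requires INR in a Table 5 subject who is still dosing.

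5. **Length of the window.** Take a continuous elevation in the Table 5 range, counted from its first detection:
   - Minimum weekly sampling: 1 confirmation + 3 weekly draws (about Days 7, 14, 21) = 4 required draws before the 4-week row can apply at Day 28. INR is required at 0 of 4.
   - Twice-weekly sampling: 1 + 7 = 8 draws, again with no required INR.
   - Dosing is once daily, so at most about 28 further doses, and only if IP is continued throughout. That is the worst case.

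6. **Event rates.** The documents do not say how many subjects would reach 3 to < 5 x ULN, how many of those would have INR above 1.5, how often the panel would be requested, or how often IP would be continued. A probability of a missed case would need all four, so none is given here.

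**The case against.** The best defence is that this is deliberate expert discretion inside a well-guarded tier. The Medical Monitor must hear of the case within 24 hours, and the same action item in Table 5 offers the panel containing INR. IP stops if the repeat is not obtained within 48 hours. Section 7.1 requires permanent discontinuation for a drug-induced liver disorder, whatever the INR. Section 2.3.1 tells investigators to discontinue readily on any suspicion of liver injury. Section 10.3.2 leaves room to report an important medical event as an SAE on judgement. The Amendment 4 entry in Appendix 13 describes the liver safety tests at this tier as something that might be triggered, so the sponsor had considered it.

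All of that stands, and it rules out three stronger readings that a reader might infer.

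- *The plan contradicts itself or is circular.* It does not and is not. INR can be ordered before any Table 6 row is met; it simply need not be.
- *Without INR nothing obliges anyone to stop IP.* Section 7.1 does so once a drug-induced liver disorder is recognised, and the other Table 6 rows still apply.
- *INR would in practice go unmeasured.* The documents cannot show this. Section 6.3.4, on the unblinded Sponsor Medical Monitor, is redacted, and the Laboratory Manual was not available. Either might bear on it.

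What the defence does not supply is a requirement to measure INR. The safeguards depend on other findings or on judgement, and the INR result is one of the things that should inform that judgement.

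**Conclusion.** The point holds as a minor, low-cost patient-safety improvement. For subjects with ALT/AST of at least 3 and below 5 x ULN, the visible protocol leaves INR optional, so Table 6's INR criterion and footnote b's SAE rule may not be evaluated while IP continues. The exposed window is one continuous episode of just under 4 weeks.

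Most likely no subject in a trial of about 100, half of them on placebo, would be affected. The benefit is insurance against a rare serious event. No endpoint, estimate or efficacy conclusion depends on it. The conclusion covers only what the readable protocol text requires, not what monitors or sites would actually do.

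**What to change.** For subjects with ALT or AST of at least 3 x ULN:

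- Add INR to Table 5's 24-to-48-hour confirmation and to its weekly repeat tests.
- Keep footnote b's exemption of anticoagulated subjects from the INR threshold; they need no weekly INR.
- Delete the words that make the Table 6 INR row conditional on a measurement having been made.

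No SAP change is needed. The by-subject laboratory and liver-event listings in SAP Section 9.2 are enough for so few subjects.

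The main cost is a protocol amendment; Amendments 3 and 4, made chiefly for liver monitoring, were classed as substantial. The assays use draws that Table 5 already requires: 4 per affected subject at weekly sampling for an elevation lasting up to Day 28. For costing only, assume 1 to 5 subjects enter the tier (1% to 5% of about 100; not a figure from the documents). That gives 1 x 4 = 4 to 5 x 4 = 20 assays, or 1 to 5 if each elevation clears at confirmation, or 8 to 40 with twice-weekly sampling. Assay prices and sample-handling costs are not in the documents.

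SAP Section 3.3 dates the last subject's completion to August 2020, so this is a comment on the protocol as written and cannot alter care in this trial.
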